## PROTOCOL AMENDMENT – SUMMARY OF CHANGES

### Amendment 1:

This amendment is considered to be substantial based on the criteria set forth in Article 10(a) of Directive 2001/20/EC of the European Parliament and the Council of the European Union.

### Overall rational for the amendment

This amendment includes changes in protocol sections to clarify clinical operation methods and to give clearer instructions to study centers in accordance with local clinical practice.

### List of Main Changes in the Amendment:

- Table 1 and Table 1 footnote in Section 1.3: Add drug screen action on Day -1 visit in the table; move weight assessment from Day 1 to Day -1; remove hematology, urinalysis, clinical chemistry test on Day 1; remove HBcAg, HbcAb related tests and contents, add serological test for *syphilis* in the footnote 'l'; remove blood samples for pharmacogenomic testing; update information of ECG testing in the footnote 'f' from "Triplicate 12-lead ECG will be performed at specified timepoints" to "Triplicate 12-lead ECG *can* be performed at specified timepoints if deemed necessary by investigator", also add text "*Timepoints for ECG evaluation from Day 1 are provided in Table 2*".
- Table 2 in Section 1.3: Remove weight, ECG, laboratory tests at pre-dose from administration on Day 1 during the in-house period; remove blood samples for pharmacogenomic testing.
- Section 1.1 and 4.1: Add "*PK sampling*" to the assessments of participants who will visit the study center on Days 6, 8, 10,12, and 15.
- Synopsis and Sections 5.1: Update "body mass index is  $\geq 18.5$  to  $26 \text{ kg/m}^2$ " to "body mass index is  $\geq 18.5$  to  $<26 \text{ kg/m}^2$ " in the inclusion criteria.
- Synopsis and Sections 5.2: Revise "average diastolic blood pressure (40-90 mmHg)" to "average diastolic blood pressure (60-90 mmHg)" in the exclusion criteria.
- Sections 8.2.3: Add information "*Triplicate 12-lead ECG can be performed at specified timepoints if deemed necessary by investigator*".

- Sections 8.7: Remove all pharmacogenomics information in the section and replace with “Pharmacogenomics assessments are not performed in this study”.
- Table 7 in Appendix 4: Remove HBcAb test and add serological test for syphilis.

In addition, minor formatting updates and corrections have been made. Such changes are not listed in this amendment.

### **LIST OF ABBREVIATIONS AND DEFINITIONS OF TERMS**

Abbreviation	Definition
AE	adverse event
AUC0-inf	area under the concentration-time curve from Time 0 to infinity
AUC0-last	area under the concentration-time curve from Time 0 to last measurable concentration
AUC0-t	area under the plasma concentration-time curve between Time 0 and the time t
BUN	blood urea nitrogen
CEN	cap-dependent endonuclease
CL/F	apparent clearance
Cmax	maximum plasma concentration
eCRF	electronic Case Report Form
IB	Investigator's Brochure
ICF	Informed Consent Form
IEC	Independent Ethics Committee
NA	neuraminidase
OTC	over-the-counter
PK	pharmacokinetic
SoA	Schedule of Activities
Tmax	time to maximum plasma concentration
T1/2	terminal elimination half-life
ULN	upper limit of normal
Vz/F	apparent volume of distribution based on the terminal phase

## 1. **PROTOCOL SUMMARY**

### 1.1 **SYNOPSIS**

**PROTOCOL TITLE:** A PHASE I, SINGLE-CENTER, OPEN-LABEL, PARALLEL, TWO DOSE LEVEL STUDY TO INVESTIGATE THE PHARMACOKINETICS, SAFETY, AND TOLERABILITY FOLLOWING A SINGLE DOSE OF BALOXAVIR MARBOXIL IN HEALTHY CHINESE VOLUNTEERS

**SHORT TITLE:** THE PK, SAFETY, AND TOLERABILITY OF BALOXAVIR MARBOXIL IN HEALTHY CHINESE VOLUNTEERS

**PROTOCOL NUMBER:** YP40902

**VERSION:** 2

**TEST PRODUCT:** Baloxavir marboxil (R07191686)

**PHASE:** I

### **RATIONALE**

The purpose of the study is to evaluate the pharmacokinetics (PK), safety, and tolerability after a single oral dose of baloxavir marboxil (40 mg or 80 mg) in healthy Chinese participants. As this is a Phase I study in healthy participants, no therapeutic benefit is anticipated for these study participants.

### **OBJECTIVES AND ENDPOINTS**

The specific objectives and corresponding endpoints/parameters for the study are outlined below.

Objectives	Endpoints/Parameters
Primary	
• To evaluate the pharmacokinetics of baloxavir marboxil and baloxavir after a single oral dose of baloxavir marboxil	

• Maximum plasma concentration (<math>C_{max}</math>)

• Time to maximum plasma concentration (<math>T_{max}</math>)

• Area under the plasma concentration-time curve (<math>AUC_{0\text{-last}}</math>, <math>AUC_{0\text{-inf}}</math>, <math>AUC_{0\text{-t}}</math>)

• Terminal elimination half-life (<math>t_{1/2}</math>)

• Apparent total oral clearance (CL/F)

• Apparent volume of distribution based on the terminal phase (<math>Vz/F</math>)

• Plasma concentration at 24 hours (<math>C_{24}</math>), 48 hours (<math>C_{48}</math>), and 72 hours (<math>C_{72}</math>)

Secondary	
• To evaluate the safety and tolerability following a single oral dose of baloxavir marboxil	

• Incidence, severity, and frequency of adverse events, serious adverse events, vital signs measurements, and clinical laboratory tests.

## **OVERALL DESIGN**

### **Study Design**

This Phase I study is an open-label, randomized, parallel-group, two dose level study in healthy Chinese participants to evaluate the PK, safety, and tolerability of baloxavir marboxil and baloxavir following a single oral administration of baloxavir marboxil.

### **Treatment Groups and Duration**

A total of 32 healthy Chinese participants 16 in each group will be enrolled in the study.

After signing the informed consent, a screening period of up to 28 days is provided to complete the study-related assessments.

During the in-house period, on confirming all the eligibility requirements, the participants will be randomly allocated to one of the two parallel groups, 40 mg or 80 mg of study drug (baloxavir marboxil). The participants will be admitted to the study center on Day -1 and receive study drug on morning of Day 1. Safety assessments and PK sampling will be carried out at scheduled timepoints. The study drug will be given after an overnight fast of approximately 10 hours followed by a fast of at least 4 hours postdose.

Participants will receive standard meals while in the study center and can be discharged at the investigator's discretion on Day 4 after the 72-hour assessments have been completed.

The participants will visit the study center on Days 6, 8, 10, 12, and 15 for *PK sampling*, safety, and other assessments such as vital signs, ECG, and laboratory test etc.

### **Length of Study**

The total duration of the study for each participant will be up to 6 weeks divided as follows:

- Screening: Up to 4 weeks
- In-house period: Day -1 to morning of Day 4
- Post-dosing and follow-up observation: Days 6, 8, 10, 12, and 15.

Participants will be admitted to the study center on Day -1 and will be discharged approximately 72 hours after the study drug administration.

### **End of Study**

The end of the study is defined as the date when the last observation of the last participant occurs and is expected  $14\pm1$  day after the dose administration of last participant, unless the participant withdraws his/her consent or withdraws early due to any other reason.

### **Data Monitoring Committee**

No Data Monitoring Committee is involved in the study.

## **PARTICIPANT POPULATION**

The study population will consist of healthy Chinese participants.

### **Inclusion Criteria**

Participants must meet the following criteria for study entry:

- Healthy male or female Chinese participants, aged 20-59 years inclusive at the time of screening. The female participants should be of non-childbearing potential.
- Chinese participants must have Chinese parents and grandparents, all of whom were born in China.
- Healthy status as defined by absence of evidence of any active or chronic disease following a detailed medical and surgical history, a complete physical examination including vital signs, 12-lead ECG, hematology, blood chemistry, viral serology, and urinalysis.
- Participants whose body weight is  $\geq 50$  to  $<80$  kg and body mass index is  $\geq 18.5$  to  $<26$  kg/m^2.
- Able to participate and willing to provide written informed consent and to comply with the study restrictions.
- Female participants must be either surgically sterile (by means of hysterectomy and/or bilateral oophorectomy) or postmenopausal for at least 1 year (defined as amenorrhea  $\geq 12$  consecutive months without another cause, and confirmed by follicle-stimulating hormone level  $> 35$  mIU/mL).

### **Exclusion Criteria**

Participants who meet any of the following criteria will be excluded at study entry:

- Participants who are considered ineligible for this study by the Principal Investigator or subinvestigator due to current or history of significant metabolic, hepatic, renal, hematological, pulmonary, cardiovascular, gastrointestinal, urological, endocrine, neurological, or psychiatric disorders with clinical manifestations.
- Participants with the following laboratory abnormalities at screening and on Day -1:
  - total bilirubin  $> 1.5 \times$  upper limit of normal (ULN)
  - AST  $> 1.5 \times$  ULN
  - ALT  $> 1.5 \times$  ULN
  - estimated glomerular filtration rate  $< 60$  mL/min/1.73 m^2 by using Cockcroft-Gault formula.
- QTc interval  $> 450$  ms (with Fridericia's correction)
- Participants with vital signs values outside of the reference range for average systolic blood pressure (90-140 mmHg), average diastolic blood pressure (60-90 mmHg), or average pulse rate (40-90 beats/minute).
- Participants with a history of stomach, vagus nerve, or intestinal surgery (except for appendectomy).
- Participants who have a history of allergic symptoms including food allergy (Note: Non-active allergic rhinitis will be allowed).

- Participants who require chronic drug therapy or those who have used drugs (e.g., prescription or over-the-counter drugs, herbal and dietary supplements, and vitamins) within 3 days prior to screening or within 14 days prior to Day -1.
- Participants who have used alcohol-containing, caffeine-containing, grapefruit containing, or St. John's wort-containing products within 72 hours prior to Day -1.
- Participants who have used tobacco- or nicotine-containing products within 24 weeks prior to screening.
- Participants who have a history of abuse of drugs and/or alcohol.
- Participants who have a positive urine cotinine, drug, and alcohol screen at screening and Day -1.
- Participants who are positive for serological test for syphilis (*Treponema pallidum*), hepatitis B surface antigen, hepatitis C virus antibody, or HIV antigen/antibody at screening.
- Participants who have donated >400 mL of blood within 12 weeks or >200 mL of blood within 4 weeks prior to screening, or have donated any amount of blood between screening and Day -1.
- Participants who have been exposed to an investigational drug within 90 days prior to the initial screening visit.
- Participants who have received baloxavir marboxil previously.
- Participants who are considered inappropriate for the study by the Principal Investigator or subinvestigator.

### **NUMBER OF PARTICIPANTS**

A total of 32 healthy Chinese participants, 16 participants in each group will be enrolled in the study. The number of participants (16 participants for each dose level) is chosen based on practical clinical judgement, the PK variability observed, anticipated drop-rate, and China's regulatory requirement. It is considered that 16 study participants in each group would provide sufficient data to characterize the PK of baloxavir and baloxavir marboxil.

### **CONCOMITANT MEDICATIONS**

[figure not shown]
The use of drugs (e.g., prescription or over-the-counter (OTC) drugs, herbal and dietary supplements, vitamins) is prohibited for 14 days prior to admission (Day -1).

The use of drugs (e.g., prescription or OTC drugs, herbal and dietary supplements, vitamins) and procedures without any medication is prohibited from admission (Day -1) until completion of the post-dosing observation period (Day 15) (or early termination if this occurs).

## 1.2 SCHEMATIC OF STUDY DESIGN

An overview of the study design is provided in [Figure 1](#).

Figure 1 Overview of Study Design

### **1.3 SCHEDULE OF ACTIVITIES**

The Schedule of the Activities is provided in [Table 1](#).

**Table 1 Schedule of Activities**

Cycle/Visit/Week	Screening	In-House					Post-Dosing and Follow-up Observation				
		Day -28 to -2	Day -1	Day 1	Day 2	Day 3	Day 4	Day 6	Day 8	Day 10	Day 15
Day	Day -28 to -2			0	24	48	72	120	168	216	264
Time Relative (h)											336
Visit Window (h)				± 2	± 2	± 2	± 2	± 24	± 24	± 24	± 24
Assessments											
Informed consent a		x									
Demographic data		x									
Medical history		x									
Height		x									
Weight	x	x					x	x			
Drug Screen b	x	x									
Randomization c			x								
Drug Administration			x								
Physical Examination d	x	x	x	x	x	x	x	x	x	x	x
Vital Signs e	x	x	x	x	x	x	x	x	x	x	x
ECG f	x	x	x	x	x	x	x				
Hematology g	x	x		x	x	x	x		x		x
Urinalysis h	x	x		x	x	x	x		x		x
Clinical Chemistry i	x	x		x	x	x	x		x		x
Coagulation test, Thyroid and Lipid profile j	x	x					x				
Pregnancy test k	x	x									x
Serology test l	x										
PK Blood Samples m			x	x	x	x	x	x	x	x	x
Admission		x									
Discharge						x					
Ambulatory visit							x	x	x	x	x
Concomitant medications	x	x	x	x	x	x	x	x	x	x	x
Adverse events n	x	x	x	x	x	x	x	x	x	x	x

eCRF = electronic Case Report Form; GGT = gamma-glutamyl transferase, h = hours; HBsAg = hepatitis B surface antigen; HCV = hepatitis C virus; PK = pharmacokinetic and TSH = thyroid stimulating hormone.

a Written informed consent for participants in the study must be obtained before performing any study-specific screening tests or evaluations.

**Baloxavir marboxil—F. Hoffmann-La Roche Ltd and Shionogi & Co., Ltd**

Protocol YP40902, Version 2

Page 16 of 74

- b Breath alcohol, urine cotinine, and urine drug screen of (amphetamines, barbiturates, cocaine, opiates, methadone, cannabinoids, and benzodiazepines) will be evaluated.
- c Participants will be randomized to 40 mg or 80 mg baloxavir marboxil in a 1:1 ratio.
- d Complete physical examination will be conducted at screening and brief physical examination will be done at other visits.
- e Vital signs include body temperature, pulse rate, blood pressure, and respiratory rate. Blood pressure and pulse rate should be measured at least 5 minutes after the participant rests in a supine position and on the same arm. Assessment of vital signs should be done prior to blood collection.
- f Triplicate 12-lead ECG *can* be performed at specified timepoints if deemed necessary by investigator. At each timepoint at which triplicate ECGs are required, three individual ECG tracings should be obtained as closely as possible in succession, but no more than 2 minutes apart. The full set of triplicates should be completed in less than 4 minutes. Electrocardiogram should be performed prior to any scheduled vital sign measurements and blood draws. In some cases, it may be appropriate to repeat abnormal ECGs to rule out improper lead placement as contributing to the ECG abnormality. *Timepoints for ECG evaluation from Day 1 are provided in Table 2.*
- g Hematology test parameters include leucocytes, erythrocytes, hemoglobin, hematocrit, platelets, differential count (neutrophils, eosinophils, basophils, monocytes, lymphocytes, other cells).
- h Urinalysis include pH, glucose, protein, and blood (leukocyte). If there is a clinically significant positive result (confirmed by a positive repeated sample), urine sample will be sent to the laboratory for microscopy and culture. If there is an explanation for the positive dipstick results (e.g., menses), it should be recorded and there is no need to perform microscopy and culture.
- i Clinical chemistry test parameters include sodium, potassium, chloride, bicarbonate, glucose (fasting), urea, creatinine, total protein, serum albumin, phosphate, calcium, total and direct bilirubin, alkaline phosphatase, ALT, AST, urate, and LDH.
- j Lipid profile includes total cholesterol and triglycerides; thyroid profile includes Free T4 and TSH; coagulation tests include INR, aPTT, and PT.
- k Blood pregnancy test will be performed at screening and urine pregnancy test will be performed at subsequent visits. If urine pregnancy test is positive it will be confirmed by blood pregnancy test. If the blood pregnancy test is positive, then the participant must be withdrawn from the study.
- l Serology tests for HIV, HBsAg, HCV and syphilis (*Treponema pallidum*) antibody will be performed.
- m Timepoints for PK samples are provided in [Table 2](#).
- n Adverse events reported from the time of signing consent up to 14 days after the last dose should be documented and recorded in the eCRFs. Any concomitant medication should also be recorded.

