### **5.2 EXCLUSION CRITERIA**

Participants who meet any of the following criteria will be excluded at study entry:

- Participants who are considered ineligible for this study by the Principal Investigator or subinvestigator due to current or history of significant metabolic, hepatic, renal, hematological, pulmonary, cardiovascular, gastrointestinal, urological, endocrine, neurological, or psychiatric disorders with clinical manifestations.
- Participants with the following laboratory abnormalities at screening and on Day -1:
  - total bilirubin  $> 1.5 \times$  upper limit of normal (ULN)

AST > 1.5 × ULN

ALT > 1.5 × ULN

estimated glomerular filtration rate <60 mL/min/1.73 m^2 using Cockcroft-Gault formula

- QTc interval >450 ms (with Fridericia's correction)
- Participants with vital signs outside of the reference range for average systolic blood pressure (90-140 mmHg), average diastolic blood pressure (60-90 mmHg), or average pulse rate (40-90 beats/minute).
- Participants with a history of stomach, vagus nerve, or intestinal surgery (except for appendectomy).
- Participants who have a history of allergic symptoms including food allergy (Note: Non-active allergic rhinitis will be allowed).
- Participants who require chronic drug therapy or those who have used drugs (e.g., prescription or OTC drugs, herbal and dietary supplements, and vitamins) within 3 days prior to screening or within 14 days prior to Day -1.
- Participants who have used alcohol-containing, caffeine-containing, grapefruit containing, or St. John's wort-containing products within 72 hours prior to Day -1.
- Participants who have used tobacco- or nicotine-containing products within 24 weeks prior to screening.
- Participants who have a history of abuse of drugs and/or alcohol.
- Participants who have a positive urine cotinine, drug, and alcohol screen at screening and Day -1.
- Participants who are positive for serological test for syphilis (*Treponema pallidum*), hepatitis B surface antigen, hepatitis C virus antibody, or HIV antigen/antibody at screening.
- Participants who have donated > 400 mL of blood within 12 weeks or > 200 mL of blood within 4 weeks prior to screening, or have donated any amount of blood between screening and Day -1.
- Participants who have been exposed to an investigational drug within 90 days prior to the initial screening visit.
- Participants who have received baloxavir marboxil previously.

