### **8.2.1 Physical Examinations**

- A complete physical examination will include, at a minimum, assessments of the cardiovascular, respiratory, gastrointestinal, dermatological, neurological, and musculoskeletal system in addition to head, eyes, ears, nose, throat, neck, and lymph nodes. Height and weight will be measured and recorded at screening. Additionally, weight will be measured on Days -1, 4, and 6. Further examination of other body systems may be performed in case of evocative symptoms at the investigator's discretion.
- A brief physical examination will include, at a minimum, assessments of the skin, lungs, cardiovascular system, and abdomen (liver and spleen).
- Investigators should pay special attention to clinical signs related to previous serious illnesses.
- Any abnormality identified at baseline should be recorded on the General Medical History and Baseline Conditions eCRF. Changes from baseline abnormalities should be recorded in participant's notes. New or worsened clinically significant abnormalities should be recorded as adverse events on the adverse event eCRF.

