#### **8.3.1 Time Period and Frequency for Collecting Adverse Event and Serious Adverse Event Information**

The method of recording, evaluating, and assessing causality of AEs and SAEs and the procedures for completing and transmitting SAE reports are provided in [Appendix 2](#).

Investigators will seek information on AEs at each visit. All AEs, whether reported by the participant or noted by study center staff, will be recorded in the participant's medical record and on the AE eCRF as follows:

**After informed consent** has been obtained **but prior to initiation of study drug**, only SAEs caused by a protocol-mandated intervention should be reported. Any other AEs should not be reported.

**After initiation of study drug:** all AEs, regardless of relationship to study drug, will be reported until 14 days after the last dose of study drug.

**Post-study adverse events and serious adverse events:** The investigator is not required to actively monitor participants for AEs after the end of the AE reporting period (14 days after the last dose of study drug).

However, if the investigator learns of any SAE (including a death) or other AEs of concern that are believed to be related to prior treatment with study drug, at any time after a participant has been discharged from the study, and the investigator considers the event to be reasonably related to the study drug or study participation, the investigator must promptly notify the Sponsor. For the procedure of reporting, see [Appendix 2](#).

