### **5.1 REPORTING REQUIREMENTS OF SERIOUS ADVERSE EVENTS AND NON-SERIOUS ADVERSE EVENTS OF SPECIAL INTEREST**

#### **Events that Occur prior to Study Drug Initiation**

After informed consent has been obtained but prior to initiation of study drug, only serious adverse events caused by a protocol-mandated intervention should be reported. The Serious Adverse Event/Adverse Event of Special Interest Reporting Form provided to investigators should be completed and submitted to the Serious Adverse Event Responsible immediately (i.e., no more than 24 hours after learning of the event).

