### **3. PERSISTENT OR RECURRENT ADVERSE EVENTS**

A persistent adverse event is one that extends continuously, without resolution, between participant evaluation timepoints. Such events should only be recorded once on the Adverse Event eCRF. The initial severity of the event should be recorded, and the severity should be updated to reflect the most extreme severity any time the event worsens. If the event becomes serious, the Adverse Event eCRF should be updated to reflect this.

A recurrent adverse event is one that resolves between participant evaluation timepoints and subsequently recurs. Each recurrence of an adverse event should be recorded separately on the Adverse Event eCRF.

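### Table 1 footnote n records adverse events from consent, Section 8.3.1 bars almost all of them before dosing, and SAP 17.1 states no onset condition for its by-dose tables

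*Protocol*

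**What the plan says.** **Collection.** Protocol Section 1.3, Table 1, marks the AE row in every column, including Screening and Day -1. Footnote n to that row reads: "Adverse events reported from the time of signing consent up to 14 days after the last dose should be documented and recorded", with the eCRFs as the place of recording.

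Section 8.3.1 sets out what goes into the participant's "medical record and on the AE eCRF as follows". For the time between consent and dosing it says "only SAEs caused by a protocol-mandated intervention should be reported. Any other AEs should not be reported". Appendix 2 Section 5.1 gives the same limit: "only serious adverse events caused by a protocol-mandated intervention should be reported". From dosing until 14 days later, all AEs are reported whatever their cause.

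Appendix 2 Section 1 ties the general AE definition to use of a medicinal product. Its list of qualifying events then adds those related to a study-required procedure, including ones before drug assignment, and does not require them to be serious.

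**Analysis.** The safety set (SAP 5.3) holds everyone who was dosed, grouped by the dose received. SAP 17.1.1 presents AE incidence by system organ class and preferred term, and by maximum severity and relationship. SAP 17.1.1.2 counts a missing relationship as related. SAP 17.1.2 and 17.1.3 add tables of serious and fatal AEs. None of these sections says when an event must have started. SAP 6.4 classes AEs that begin on the dosing date as post-baseline, but 17.1 makes no use of that split. SAP 8 and 17.1 leave output detail to templates that are not among the documents.

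**The concern.** Two current instructions about AE recording disagree. A site working from the schedule would enter events that Section 8.3.1 tells it not to report. The safety set selects participants and not events, so nothing in the SAP text would take those entries out of the tables once the participant is dosed.

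AE incidence is a secondary endpoint, summarised in two groups of 16 with no placebo arm. An event that preceded the drug would then stand in a dose column. If causality was left blank, it would also stand in the drug-related rows. The error would overstate risk. Randomisation takes place on Day 1 just before the dose (Table 2), so it is not expected to favour either dose.

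**Working it through.** The plan states no figure on this point, so the check is mainly a comparison of texts.

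**1. Do the collection rules conflict?**
- Footnote n: from consent, AEs without restriction, in the eCRFs.
- Section 8.3.1: before dosing, procedure-caused SAEs only; its lead-in names the AE eCRF.
- Appendix 2 Section 5.1: same limit as 8.3.1.
- Appendix 2 Section 1: procedure-related events before drug assignment are AEs, serious or not.

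The marks in the Table 1 row could fit 8.3.1, because procedure-caused SAEs must be captured at those visits. The conflict lies in the wording of the footnote. The clearest case is a non-serious procedure-related event before dosing: an AE under Appendix 2 Section 1, recorded under footnote n, barred by 8.3.1.

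**2. How would such an event reach a by-dose table?** Three conditions must all hold.
- It is entered on the AE page. This is so under footnote n, but not under 8.3.1 unless it is a procedure-caused SAE.
- The participant is later dosed. Screen failures never enter the safety set.
- No onset filter applies. The SAP text has none; the templates cannot be checked.

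**3. How large is the shift?** With 16 dosed per group, k participants whose only AE is pre-dose add k/16:
- k = 1: 1/16 = 6.25 percentage points
- k = 2: 2/16 = 12.5 percentage points

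For non-serious events under 8.3.1, k = 0 and the shift is 0.

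**4. How likely is at least one?** The documents give no pre-dose AE rate. Assume footnote n is followed and each participant independently has a recorded pre-dose AE with probability p. The chance of at least one among 32 is 1 - (1 - p)^32:
- p = 1%: 27.5%
- p = 2%: 47.6%
- p = 5%: 80.6%
- p = 10%: 96.6%

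These values of p are assumptions without support in the documents. The results are upper limits for a change in overall AE incidence, because a participant who also has a post-dose AE is counted anyway.

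**The case against.** The strongest reply is that the protocol shows which text governs. Section 8.3 requires AEs to be recorded and reported as that section and Appendix 2 direct, and Section 8 describes the schedule as a summary of procedures and timepoints. The limit is stated in both places that Section 8.3 names. This makes 8.3.1 the better reading, but it does not remove a footnote that tells site staff something else.

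A reader might infer that any mild symptom that comes and goes between screening and dosing would be counted. The documents do not clearly support that. The general definition concerns participants who have been given a product, so an unrelated pre-dose symptom is doubtful as an AE at all. Section 8.2.1 adds: "Any abnormality identified at baseline should be recorded on the General Medical History and Baseline Conditions eCRF". Anyone who used drugs "within 3 days prior to screening or within 14 days prior to Day -1" is excluded, which further limits the events at issue among dosed participants.

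A reader might also infer that pre-dose SAEs enter the tables under either rule. That route is weak. Appendix 2 Section 5.1 sends pre-dose SAEs to a reporting form and later ones to the eCRF, while SAP 17.1.2 counts only SAEs marked on the AE page. The lead-in of 8.3.1 leaves entry possible, but such a participant would still have to qualify as healthy and be dosed.

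Finally, the missing templates could contain a filter. That stands as a limit on what can be claimed: the SAP text states no onset condition, and no more than that can be shown.

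**Conclusion.** The inconsistency is real and in current text, and the SAP text does not neutralise it. If the site follows footnote n and the templates hold no filter, each dosed participant whose only AE is pre-dose adds 6.25 points to one group's incidence. If 8.3.1 is followed, the effect is near zero. No hypothesis is tested and the primary PK endpoints are not affected. Minor.

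It is tempting to express the size as a relative inflation. Set against the Phase I rates in Section 4.3, one extra participant would raise the count by about 44% (2 of 14, or 16 x 2/14 = 2.29 per group; 1/2.29) down to about 9% (10 of 15, or 10.67 per group; 1/10.67). That range shows the effect of one assumed event and does not measure the defect. Both of those rates are from a 20 mg study, and none of the Phase I rates there is like-for-like with this one.

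**What to change.** **Protocol.** Reconcile footnote n, the Table 1 AE row and the Appendix 2 Section 1 item on procedure-related events with Section 8.3.1 and Appendix 2 Section 5.1, so that one pre-dose collection rule applies.

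**SAP 17.1.**
- Limit the by-dose AE, severity, relationship and SAE tables to events with onset on or after the dosing date, consistent with SAP 6.4.
- Treat a missing or partial onset date as post-dose unless its known parts show otherwise. SAP 7.3 and SAP Appendix 2 cover medications and non-drug treatments only.
- List pre-dose events separately.
- Leave the fatal-AE table and the death outputs unfiltered. Protocol Appendix 3 Section 3 keeps a persistent event on a single record, where "the severity should be updated to reflect the most extreme severity any time the event worsens", and describes no date of worsening. An onset filter could therefore drop an event that began before dosing and proved fatal afterwards.

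For the same reason, a non-fatal event that began before dosing and worsened later would appear only in the pre-dose listing; a line in the SAP should say so.

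**Cost.** One footnote and row edit, one clarification in Appendix 2, one SAP paragraph and one listing. Only the AE onset date is needed. If collection has already ended, the SAP part can be made alone.
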